6.4 WEEK 26 ANALYSIS

The protocol mentioned that a formal week 26 analysis for the primary efficacy endpoint (the 2 comparisons between the vadadustat groups and Micera with hierarchical testing) may be conducted after the last patient completes the primary efficacy period (Week 26). Because of the complete response letter received in March 2022 from FDA regarding the Vadadustat NDA 215192 , Akebia decided not to conduct this week 26 analysis.

6.5 SUBJECT DISPOSITION

The number and percentage of subjects randomized and included in each analysis population will be summarized by treatment group and overall. Reasons for excluding subjects from the analysis populations will be presented in a by-subject listing.

The number of randomized subjects who completed study medication treatment, discontinued from study medication early, and completed or discontinued from the study and reasons for discontinuation will be summarized by treatment group and overall.

Time to study treatment discontinuation will be estimated using the Kaplan-Meier product-limit method and log rank test as described in [Appendix A](#). Subject completed

study treatment will be censored at date of study completion. The hazard ratio and corresponding 95% confidence interval for the comparison of vadadustat to and Mircera control group will be estimated using a Cox proportional hazards model, with treatment group, randomization stratification factor (dialysis organization), and baseline Hb as covariates. Kaplan-Meier plot of time to study treatment discontinuation will be provided.

6.6 PROTOCOL DEVIATIONS

Definitions of important and non-important protocol deviations will be described in a master Protocol Deviation log file, including those protocol deviations leading to exclusion from the PP populations. These will be specified prior to database lock on a blinded basis.

Protocol deviations will be summarized in the randomized population as the number and percentage of subjects with a protocol deviation by treatment group and overall. A by subject listing of protocol deviations, indicating those exclusionary from the PP population, will be provided.

6.7 DEMOGRAPHIC AND BASELINE CHARACTERISTICS

The following item will be summarized by treatment group and overall based on randomized population:

Demographic variables: age, age group 1 (<65 years, \geq 65 years), age group 2 (\geq 18-64 years, \geq 65-84 years, \geq 85 years), sex, ethnicity, race, height, pre- and post-dialysis weight, body mass index (BMI)

BMI (kg/m^2) = weight (kg)/(height (m))at Screening V2

Baseline characteristics: stratification factor (Dialysis organization), Mircera monthly dose amount, Baseline IV/Oral iron dose use (mg/week), Kt/V result, history of diabetes mellitus, cardiovascular disease, retinal disorder, statin used, systolic blood pressure (SBP), diastolic blood pressure (DBP) and heart rate.

Baseline Laboratory Measurements: Hb, hepcidin, iron indices (ferritin, TSAT, TIBC, serum iron), serum glucose, lipid profile (total cholesterol, low-density lipoprotein (LDL), high-density lipoprotein (HDL), triglycerides) and CRP.

Continuous variables will be summarized as descriptive statistics. Categorical variables will be summarized by using number and percentage.

6.8 MEDICAL HISTORY

Medical history terms will be coded using the Medical Dictionary for Regulatory Activities (MedDRA), and the number and percent of subjects with medical history will be summarized by system organ class (SOC) and preferred terms (PT) for each treatment group and overall based on the safety population.

Etiology of CKD and dialysis history will be summarized by treatment group and overall based on safety population.

6.9 PRIOR AND CONCOMITANT MEDICATIONS

Prior and concomitant medications will be coded using World Health Organization Drug dictionary (WHO DD). Data collected from eCRF page “Prior and Concomitant Medications” and “ESA Administration” will be included and summarized for each treatment group and overall based on the safety population. Anti-Hypertensive Medications will be summarized for each analysis period by treatment group and overall based on the safety population.

Prior medications will be defined as any medications that were taken 30 days prior to SV1 to before the first dose of study medication. Concomitant medications will be defined as any medications taken on or after first dose of study medication.

6.10 STUDY DRUG DOSING AND COMPLIANCE

Due to differences in data collection between the two treatment groups, the calculated compliance rate for a given time period will be derived differently for each treatment group:

Compliance rate for vadadustat group (%) = (treatment duration in the given time period (+ 7/3, if the treatment duration in the give time period is not multiple of 7 days)– number of missed dose during the given time period*7/3)/(treatment duration in the given time period (+ 7/3, if the treatment duration in the give time period is not multiple of 7 days))*100.

Any tablet is taken in a day will be considered compliant for that day.

Compliance rate for Mircera group (%) = Sum of minimum (treatment duration of the dosing record + the dosing frequency for the exposure, treatment duration up to the start date -1 of the next dosing record) during the give time period/(treatment duration in the given time period + the dosing frequency of the last dosing record in the given time period for the exposure)*100.

Total duration (week) of dose exposure and interruption will be provided by treatment group for safety population.

The following summary will be provided by treatment group for both safety population and FAS as well:

- Study Treatment Compliance Rates by analysis period
- Average weekly dose by analysis period
- Number of subjects who took vadadustat by dose level and by analysis visit
- Maximum increase in dose amount of Mircera by analysis period
- Study treatment modifications and discontinuations

6.11 EFFICACY ANALYSES

The general approach for analysis of continuous outcomes will be analysis of covariance (ANCOVA) with multiple imputation for missing data or mixed models for repeated measurements (MMRM) on observed data.

For binary variables, the general approach will be Mantel-Haenszel estimation of risk difference stratified by dialysis organization with or (without) multiple imputation for handling missing data [Mantel, 1959].

6.11.1 Primary Estimand

The primary estimand defining the treatment effect of interest in this trial uses the treatment policy strategy specified in the [ICH E9 \(R1\) Addendum \[FDA 2021\]](#). In this trial, the research question is to compare the assignment of Mircera to vadadustat, regardless of intercurrent events. The primary analysis will be performed in the randomized population in accordance with intent-to-treat. This means the analysis will include individuals who never received treatment, discontinued treatment, were rescued with any therapy, and withdrew consent. The estimate of the treatment effect of interest will be the one regardless of whether the intercurrent event occurred.

The primary estimand for this trial is defined by the following components:

- Treatment: vadadustat with rescue therapy as needed versus Mircera with rescue therapy as needed
- Population: randomized population.
- Variable: change in Hb from Baseline (average pretreatment Hb) to the primary evaluation period (average Hb from Weeks 20 to 26, inclusive).
- Intercurrent event: never received treatment, discontinued treatment, rescued with any therapy or withdrew consent.
- Population-level summary: difference in mean change in Hb from baseline to the primary evaluation period between the vadadustat groups and Mircera control group.

6.11.2 Primary Efficacy Analyses

The primary efficacy endpoint is defined as the mean change in Hb between Baseline (average pretreatment Hb) and the primary evaluation period (average Hb from Weeks 20 to 26, inclusive).

The primary analysis of the primary endpoint will use the randomized population with imputation of data. All intercurrent events will be handled by treatment policy strategy ([Section 6.11.1](#)). Unobserved data after intercurrent events, including Hb outcomes and any covariates to be used in the models, will be imputed with the randomized treatment group to which the subject was randomized using multiple imputation under fully conditional specification (FSC) method as described in [Appendix B](#). Data up to

scheduled visit of week 26 will be included in the primary efficacy analyses. Analysis of covariance (ANCOVA) as described in [Appendix A](#) will be used to calculate the LS mean (SE) by treatment group and LS mean difference (SE), 95% confidence intervals (CI) of the difference in mean change in Hb from baseline to the primary evaluation period between the vadadustat groups and Mircera control group, with the randomization stratification factor (Dialysis organization) and Baseline Hb as covariates.

Treatment comparisons will be performed between the vadadustat and Mircera groups. Subjects in the vadadustat starting dose groups of 600 mg or 900 mg TIW will have their doses adjusted to maintain Hb levels of 10.0 to 11.0 g/dL following the protocol's dosing algorithm.

- Noninferiority of vadadustat will be established if the lower limit of 2-sided CI is greater or equal to -0.75 g/dL for combined vadadustat dosing groups minus Mircera.

If the lower limit of the 2-sided 95% confidence interval for the difference between the mean Hb change from baseline to Weeks 20 to 26 in the vadadustat group and the mean Hb change from baseline in the Mircera group is above zero, superiority will have been established and the finding will be interpreted as providing evidence of a greater change from baseline in Hb for vadadustat relative to the control arm. Because the same 95% confidence interval is used to the superiority test, no adjust of multiplicity is needed.

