Vadadustat has shown dose-dependent increases in EPO concentrations in Phase 1 and Phase 2a studies. The changes in EPO have been accompanied by an increase in reticulocytes and Hb as well as increases in TIBC and decreases in hepcidin and ferritin. Data from Japan Phase 3 studies in NDD-CKD and DD-CKD subjects and post-hoc analyses of the US Phase 2 DD-CKD study indicate the potential for an association between higher baseline ESA dose and a lower Hb response among subjects converted from ESA to vadadustat. Overall, the safety profile for vadadustat has been acceptable and has supported further development. Vadadustat has demonstrated consistent bioavailability with area under concentration-time curve (AUC) and maximum observed concentration (C_{max}) in Phase 1 and Phase 2 studies covering the dose range of 80 to 1200 mg after single administration and 500 to 900 mg after repeated daily administration for 10 days. The plasma half-life of vadadustat had a modest increase in subjects with NDD-CKD and DD-CKD. Despite the longer half-life in the CKD group, vadadustat plasma concentrations are not expected to accumulate with repeated QD or TIW administration.

Vadadustat is extensively metabolized and its metabolites are eliminated from the body by dual routes of excretion (both renal and fecal). The urinary excretion of vadadustat and its metabolites has been shown to be less than 60% in healthy human subjects. In a clinical study conducted to evaluate the effect of hemodialysis on the exposures to vadadustat, hemodialysis did not have an

effect on the exposures of vadarustat or its metabolites. Given its short half-life and the dual routes of elimination, vadarustat is unlikely to accumulate in patients with CKD.

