Multiple doses of up to 900 mg daily for up to 10 days and single doses of 1200 mg have been examined in healthy subjects. Vadarustat demonstrated dose-proportional PK and dose-dependent serum EPO concentrations that returned to baseline levels with treatment cessation. A higher incidence of adverse events (AEs) in the gastrointestinal System Organ Class (SOC) – nausea, diarrhea, abdominal pain, dyspepsia – was observed in groups treated with 700, 900, or 1200 mg compared with lower vadarustat doses or placebo. Most AEs were mild to moderate, short-lived (1 or 2 days), and assessed as unrelated by investigators. No AEs led to study withdrawal, and no serious adverse events (SAEs) were reported in healthy subjects. No clinically meaningful changes or abnormalities in vital signs, safety laboratory studies, or electrocardiogram (ECG) parameters were reported.

A 16-week, open-label, multicenter, Phase 2 study evaluated vadarustat in 94 subjects receiving chronic hemodialysis previously maintained on epoetin alfa and intravenous (IV) iron from the 3 months prior to Screening. Epoetin alpha was discontinued and subjects were assigned to 1 of 3 vadarustat dose cohorts: 300 mg QD, 450 mg QD, or 450 mg TIW. Dosing was fixed for the first 8 weeks; for the subsequent 8 weeks dose was adjusted from 150 to 600 mg according to Hb response based upon a dose adjustment algorithm. Sixty-nine of the 94 subjects completed the study. The primary endpoint was the mean Hb concentration change from pre-treatment average (Screening Visit 1 [SV1], Screening Visit 2 [SV2], and Baseline Visit) to mid-study (Weeks 7 to 8) and end-of-study (Weeks 15 to 16) and was analyzed using observed Hb values (no imputation for missing data). No statistically significant mean change in Hb from pre-treatment average was observed for either of the 2 time points for any of the three treatment groups.

Among subjects randomized to an initial dose of 300 mg QD, 450 mg QD, or 450 mg TIW, 0% (0 of 30), 3% (1 of 33), and 19% (6 of 31) of subjects withdrew from the study due to worsening anemia, respectively. In a sensitivity analysis using last observation carried forward for the primary efficacy endpoint, no significant mean change in Hb from pre-treatment levels was observed in the 300 mg daily dosing group. At Weeks 15 to 16, modest, statistically significant mean decreases were observed in the 450 mg daily and 450 mg TIW dosing groups.

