In a post-hoc univariate analysis of baseline characteristics, higher pre-baseline epoetin alfa dose was associated with a decrease in mean Hb at Weeks 7 to 8 and Weeks 15 to 16 in the dosing cohorts. Subjects who discontinued the study due to worsening anemia had a higher mean pre-baseline epoetin alfa dose compared with subjects who discontinued due to other reasons or subjects who completed the study.

A total of 34 Akebia studies spanning Phase 1 through 3 have been completed or are ongoing. In the studies completed to date (Phase 1 and 2 studies), a total of 1011 subjects have received vadarustat, including 553 healthy subjects, 450 subjects with CKD, and 8 subjects with hepatic impairment. In 4 ongoing Phase 3 studies, 7237 subjects have received study medication (vadarustat or comparator).

Generally, in completed vadarustat studies with healthy subjects, there were a low number of AEs. The most frequently reported AEs in healthy subjects were in gastrointestinal disorders (nausea, diarrhea, abdominal pain, flatulence, dyspepsia) and nervous system disorders (headache, dizziness). The majority of the events were mild to moderate in severity. There were

no SAEs, deaths, or withdrawals due to AEs. [REDACTED]

[REDACTED] vital signs, or ECGs.

In completed Phase 2 studies, the most frequently reported AEs in subjects with CKD were in gastrointestinal disorders (nausea, diarrhea, vomiting), CV disorders (hypertension, hypotension, coronary artery disease), renal disorders (renal failure chronic, renal failure acute), infections and infestations (gastroenteritis, urinary tract infection, pneumonia), and metabolism and nutrition disorders (hyperkalemia, fluid overload).

The INNO₂VATE program is the global phase 3 clinical development program comprised of 2 studies in subjects with DD-CKD in which vadadustat and the comparator ESA, darbepoetin alpha, were studied. In this program, vadadustat was titrated up or down from a starting dose of 300 mg according to Hb response. The primary safety endpoint of the INNO₂VATE program was a MACE endpoint and vadadustat demonstrated non-inferiority to darbepoetin alpha in this regard.

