There were 266 (15.0%) and 276 (15.6%) subjects that experienced TEAEs resulting in death in the vadadustat and darbepoetin alfa treatment groups, respectively. The most frequent TEAEs by PT resulting in death were similar between both treatment groups, and included cardiac arrest (2.0% and 2.1%), septic shock (1.3% and 1.2%), and cardio-respiratory arrest (1.2% and 1.3%) for the vadadustat and darbepoetin alfa treatment groups, respectively.

In the vadadustat treatment group, all deaths due to TEAEs were considered unrelated. In the darbepoetin alfa treatment group, only 1 death due to TEAE of acute MI was considered related. The TEAEs that resulted in death were similar across both treatment groups.

In addition to Study CI-6548-0017, Study CI-6548-0025, a Phase 2, randomized, open-label study to evaluate vadadustat for the treatment of anemia in hemodialysis subjects converting from epoetin alfa therapy, has recently completed the active patient phase but summary efficacy and data are not available at this time. Subjects who were randomized to vadadustat were treated QD from Day 1 to Week 12 and if Week 12 criteria were met, then vadadustat was administered TIW from Weeks 12 to 20. Dose levels of vadadustat administered in this study include

150, 300, 450, 600, 750 and 900 mg QD or TIW. One hundred twenty-nine subjects were randomized to vadadustat and 36 subjects were randomized to epoetin. All randomized subjects received at least one dose of study drug. Of the randomized subjects, 60.5% of subjects in the vadadustat group and 88.9% of subjects in the epoetin group completed treatment and 76.7% of subjects in the vadadustat group and 94.4% of subjects in the epoetin group completed the study.

Overall, taking into account the entire vadadustat clinical development program, the safety profile to date supports the ongoing clinical development of vadadustat as an orally bioavailable agent for the treatment of anemia associated with CKD.

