5.2 Scientific Rationale for Study Design

This study will evaluate the efficacy and safety of dose conversion from a long-acting ESA (Mircera) to TIW vadadustat for the maintenance of treatment of anemia in hemodialysis patients. Numerous studies have demonstrated that hemodialysis subjects requiring higher ESA

doses to treat their anemia have a higher burden of comorbidities, a more inflammatory state, and a greater risk of adverse outcomes (Besarab 1998; Parfrey 2005; Unger 2010). As described above (Section 3.4) in a Phase 2 hemodialysis study (CI-0011), a post-hoc analysis suggested higher pre-baseline ESA doses were associated with lower observed mean Hb levels. Subjects on higher pre-baseline ESA doses may benefit from a higher starting dose of vadadustat after initial conversion from ESAs.

In this study, Mircera was chosen as an active comparator as it is a long-acting Continuous EPO Receptor Activator (CERA) and therefore can be administered less frequently than short- and middle-acting ESAs, while maintaining equivalent efficacy for the treatment of anemia in patients with CKD (Biggar, 2017; Davey, 2018; Mircera USPI 2018; Palmer, 2014). Patients receiving CERA required less frequent ESA administration, demonstrated smaller decreases in Hb levels, and were less likely to require an ESA dose during hospitalization. Overall, CERA showed comparable clinical performance to shorter-acting ESAs while reducing dose frequency in CKD patients receiving hemodialysis (Davey et al, 2018).

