Hb monitoring, a dose adjustment algorithm ([Section 7.1.2](#) and [Appendix 1](#)), and phlebotomy will be implemented to mitigate the potential risk of a rapid Hb rise, as follows:

- Hb measurements are scheduled at least every 2 weeks to Week 8 and thereafter every 4 weeks.
- The dose adjustment algorithm will target a narrow Hb range, 10.0 to 11.0 g/dL.
- The protocol specifies that phlebotomy may be considered in the setting of high Hb levels (>14.0 g/dL) or a high Hb rate of rise, based on the investigator's judgment.

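### Baseline Mircera dose, which the protocol links to Hb response after conversion, enters no readable efficacy analysis; adding it is a low-cost improvement, not the repair of an error

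*SAP*

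**What the plan says.** **Where the dose appears.** Protocol 9.10.2 has the ESA regimen before randomization recorded. SAP 6.7 tabulates monthly Mircera dose as a baseline characteristic. SAP 6.1 defines a conversion of Mircera to epoetin-equivalent U/kg/week.

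**Where it does not appear.**
- The primary ANCOVA is fitted "with the randomization stratification factor (Dialysis organization) and Baseline Hb as covariates" (SAP 6.11.2; protocol 10.5.2 agrees).
- The MMRM terms listed in SAP 6.11.2.1 are baseline Hb, dialysis organization, treatment, period and two interactions.
- The subgroups are age, sex, race and dialysis organization (protocol 10.6.7). SAP 6.14 adds baseline Hb.

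**What the protocol says about prior dose.** In protocol 3.4, the Japanese Phase 3 data and post-hoc analyses of the US Phase 2 dialysis study "indicate the potential for an association between higher baseline ESA dose and a lower Hb response among subjects converted from ESA to vadadustat". In that Phase 2 study, "Subjects who discontinued the study due to worsening anemia had a higher mean pre-baseline epoetin alfa dose" than those who left for other reasons or completed. Protocol 5.2 carries this into the design rationale: "Subjects on higher pre-baseline ESA doses may benefit from a higher starting dose of vadadustat" after conversion.

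**Missing data.** Subjects who stop study drug permanently leave the study (protocol 8.1.2). Their later Hb is multiply imputed under missing at random, with a tipping-point analysis in steps of 0.1 g/dL (SAP Appendix B.3). The imputation code is redacted.

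**The concern.** The trial tests conversion from Mircera. Prior ESA dose is the baseline factor that the protocol singles out as possibly predicting how a converted patient responds, and no readable efficacy analysis uses it. The documents give no reason for leaving it out.

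Three things could be at stake, in order of weight:

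1. **Effect modification.** SAP v1.1 made the primary contrast both vadadustat groups combined against Mircera. The comparisons by starting dose are now exploratory, and none of them looks at prior dose. The question raised in protocol 5.2, whether patients on higher prior doses respond differently, would go unexamined.
2. **Imputation.** If dose predicts both dropout and Hb beyond the observed Hb values, and is not in the imputation model, imputed vadadustat values come out slightly high. That direction favours noninferiority.
3. **Precision.** A prognostic covariate can narrow the confidence interval.

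**Working it through.** **Inputs.** From SAP 3.3: SD 1.2 g/dL, margin -0.75 g/dL, true difference 0, 150 per arm, 30% dropout. Evaluable: 150 x 0.7 = 105 per arm, so 210 vs 105 for the combined contrast. The documents give no correlation between dose and Hb change and no dropout slope; every r and odds ratio below is an assumption.

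**1. The plan's own figure.** Pairwise, SE = 1.2 x sqrt(2/105) = 0.1656 and power = Phi(0.75/0.1656 - 1.96) = 99.5%. Combined, SE = 1.2 x sqrt(1/210 + 1/105) = 0.1434 and power = 99.9%. The stated power of more than 90% is met with room to spare.

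**2. Precision, link equal in all arms.** Half-width = 1.96 x 1.2 x sqrt(1 - r²) x sqrt(1/210 + 1/105).

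| r | Half-width (g/dL) |
|---|---|
| 0 | 0.281 |
| 0.1 | 0.280 |
| 0.3 | 0.268 |
| 0.5 | 0.243 |

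At r = 0.3, power at an assumed true difference of -0.3 rises from about 88% to 90.8%.

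**3. Precision, link on vadadustat only (r = 0.3).** This is the case closest to the evidence, which concerns converted subjects.
- Common slope: the pooled slope is (210 x 0.3 + 105 x 0)/315 = 0.2 SD. Variance factors are 1 - 2(0.2)(0.3) + 0.04 = 0.92 on vadadustat and 1.04 on Mircera. Since 0.92/210 + 1.04/105 = 1/210 + 1/105, the half-width stays at 0.281: no gain.
- Dose-by-treatment term: 1.96 x 1.2 x sqrt(0.91/210 + 1/105 + 0.09/315) = 0.280. The last term arises because mean dose is itself estimated; dropping it would give 0.277 and overstate the gain.

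**4. Cost of an uninformative covariate.** With 315 evaluable, sqrt(310/309) = 1.0016, so the interval is about 0.16% wider.

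**5. Imputation bias in the vadadustat mean.** Simulation of 1,000,000 subjects: dose-Hb correlation 0.3 (higher dose, lower Hb), Hb-Hb correlation 0.6, logistic dropout on dose, regression imputation without dose. Dropout is 30% (SAP 3.3) or 39.5% (100 - 60.5, protocol 3.4). Simulation error is about 0.002.

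| On-treatment Hb values in model | 30%, OR 1.5 / 2.0 per SD | 39.5%, OR 1.5 / 2.0 per SD |
|---|---|---|
| None | 0.044 / 0.068 | 0.055 / 0.090 |
| One | 0.016 / 0.028 | 0.023 / 0.037 |
| Three | 0.008 / 0.013 | 0.011 / 0.017 |
| Six | 0.004 / 0.006 | 0.007 / 0.009 |

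With dose in the model the bias is 0 within simulation error. It is also 0.00 if dropout follows an observed Hb that is in the model. The lower rows are the likely ones: "Hb measurements are scheduled at least every 2 weeks to Week 8 and thereafter every 4 weeks", which gives six scheduled values from Week 2 to Week 16.

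**6. In tipping-point units.** Bias divided by the missing fraction is the equivalent shift among missing subjects. With one to three Hb values it runs from 0.008/0.30 = 0.03 to 0.037/0.395 = 0.09 g/dL; with none, from 0.14 to 0.23. All of these fall within the first one to three steps of 0.1.

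**7. What a dose subgroup can show.** With a median split, each half has 105 vadadustat and 52.5 Mircera subjects. Half-width within a half: 1.96 x 1.2 x sqrt(1/105 + 1/52.5) = 0.40 g/dL. For the difference between halves: 1.96 x 1.2 x sqrt(2 x (1/105 + 1/52.5)) = 0.56 g/dL.

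**The case against.** The case against acting is substantial.

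- **The ANCOVA is valid as planned.** It adjusts for the stratification factor and baseline Hb, and randomization protects it. Which further prognostic covariate to add is discretionary. This stands.
- **Power is not short.** It is 99.9% at the planned difference, and nothing in the documents shows that prior dose predicts Hb in patients who stay on Mircera. If it does not, a common-slope covariate buys no precision. This stands, so precision cannot carry the point.
- **The tipping-point analysis already covers the missing-data risk.** For shifts of the size computed above, it does.
- **The evidence is thin.** It is described as potential, is partly post hoc and partly about epoetin, and the entry cap of 250 micrograms per month narrows the dose range. This limits the expected effect but does not remove the reason to look.
- **Redaction.** Most of Appendices A and B is unreadable, so dose may already be in a model. This too stands; the point is confined to the readable text.
- **Timing.** The trial is open-label and SAP v1.1 has already changed the primary contrast, so a further change to the primary model needs care. The fix allows for this.

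A reader might infer more: that leaving dose out tilts the primary result towards noninferiority. The documents do not support that. They do not show that dose is missing from the imputation model. In the Phase 2 study, "19% (6 of 31) of subjects withdrew from the study due to worsening anemia", but that was on 450 mg TIW, below both starting doses here, and dropout for worsening anemia is largely visible in the Hb values themselves. In the later study "60.5% of subjects in the vadadustat group and 88.9% of subjects in the epoetin group completed treatment", but "76.7% of subjects in the vadadustat group and 94.4% of subjects in the epoetin group completed the study", and neither figure is broken down by prior dose. ESA rescue in this trial interrupts vadadustat rather than ending it (protocol 7.5.5.2).

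**Conclusion.** The point holds as a worthwhile, low-cost improvement. It does not show an error in the plan and does not threaten the validity of the primary result.

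- **Main reason:** the protocol names prior ESA dose as a possible modifier of response after conversion, and no readable efficacy analysis examines it. Pooling the two starting doses makes that gap more noticeable.
- **Second reason:** the missing-at-random assumption is more credible with dose in the imputation model. The bias avoided is likely 0 to 0.02 g/dL with several on-treatment Hb values, and 0.00 if dropout follows observed Hb.
- **Precision** is a bonus at most: 0.281 to 0.268 g/dL at r = 0.3 with an equal link in all arms, and essentially nothing if the link exists only on vadadustat.

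These sizes rest on assumed correlations and dropout slopes. The conclusion that the omission is small but cheap to mend holds over the ranges shown.

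**What to change.** Settle these before any by-treatment results are seen:

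1. **Define one baseline Mircera dose**, for example the log of mean monthly dose over the 8 weeks before the second screening visit, or the SAP 6.1 conversion.
2. **SAP 6.14:** add a subgroup at or below versus above the median dose, and a treatment-by-dose estimate. Label both descriptive; with a half-width of about 0.56 g/dL the interaction cannot be confirmatory.
3. **Appendix B:** state whether dose is in the imputation model. If not, add it by randomized arm. A common slope would leave 35% to 44% of an arm-specific bias in the scenario with no on-treatment Hb, and an ANCOVA term does not repair the imputation.
4. **SAP 6.11.2:** add dose as an ANCOVA covariate. If by-treatment results may already have been seen, keep the planned model as primary and report the dose-adjusted ANCOVA beside it as supplementary.

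The cost is one derivation from data already collected, a few model terms and about 1 degree of freedom (interval about 0.16% wider if dose is uninformative). In a linear ANCOVA the estimand does not change, and SAP 6.11.2 already provides for imputing missing covariates.
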